# **1 MATERIAL AND METHODS**

#### 1.1 Study Design

This will be a double-blind, placebo controlled randomized controlled trial. Morbidly obese men and women with IR who are eligible for bariatric surgery but did not perform such procedure will be approached. Those consenting will be randomly assigned to either allogenic FMT (prepared from stool donated by healthy lean donors with BMI <23 kg/m^2, matched for gender with the recipient) or autologous FMT (re-infusion of own collected feces; placebo). We plan to randomize 30 patients. Stool, blood, anthropometric measurements, questionnaires, quality of life, depression and anxiety will be assessed and will be collected before FMT and at 1 and 3 months post FMT. At baseline a physical examination will be performed, and will also be preformed if symptoms are present 3-months post-FMT . OM will be assessed before FMT and 3-months post FMT. Intestinal mucosa biopsies will be collected during colonoscopy for FMT administration as well as samples for safety.

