#### Participant withdrawal criteria:

#### All participants:

Any participant may discontinue from the study at any time:

- At the discretion of the investigator
- At the request of the participant (drop-out)

The reason for discontinuation will be clearly documented in the relevant Case Report Form (CRF).

The following will result in withdrawal of a participant from the study:

- Significant non-compliance with the protocol, based on the investigator's judgment following discussion with the study team and/or a co-investigator
- Any other situation where, in the opinion of the investigator, continued participation would NOT be in the best interest of the participant.

In the event that the participant discontinues the study due to a serious adverse event (SAE), a follow-up contact will be made. This contact will be documented in the source document.

If a participant fails to appear for a follow-up examination, up to three documented phone calls and/or registered mail will be used to locate and recall the participant, if possible.

Specific criteria for FMT recipients: Only one single dose of study product will be administered. Patients will be withdrawn from the study, if the FMT cannot be administered for any reasons. Data of these patients will not be included in the study, except for comparison with the patients who did receive the FMT. These patients will be replaced through additionally randomized patients. There will be no follow-up for patients who did not receive FMT.

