### **1.7 Statistical Considerations**

### 5.7.1 Sample size and power calculations

Our sample size is determined based on current literature, feasibility and the experience of team members, due to the pilot nature of the proposed study. Following common practice for this kind of studies (e.g. (179, 180)), we plan to recruit until we have randomized 36 eligible patients (18 per FMT

group). With a 20% attrition rate we assume that 15 patients per group will finish the intervention. This represents a greater sample size than the only previous FMT study on metabolic syndrome (26). We are confident that this sample size will allow us to investigate the stated aims.

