### 5.8 Randomization and blinding

# 5.8.1 Randomization list and blinding

Allocation concealment will be maintained by the lab technologist at the UHN-SHS FMT program, who will prepare the fecal filtrates for each patient but will otherwise not be involved in the conduct or analysis of the study. The allocation list will be kept in sequentially numbered envelopes with the group assignments. The group assignments will be based on a blocked randomization list (4 patients per block), created in SAS proc PLAN. The list will be created to randomize 60 patients, even though 36 are planned to be randomized. As we are including only dosed patients in the analysis, this will allow us to randomize additional patients, in case the FMT is not conducted in participants after they were randomized. The list is created by a person at the UHN, who will not be involved in conduct or analysis of the study. The technologist will have to date and sign the opened envelope.

The technologist will open the allocation on the day the patients at providing their baseline stool sample. Only if the patient is allocated to autologous FMT, a fecal filtrate from the patient's own feces is produced. On the day of the FMT, the bags with the fecal filtrate will be provided to the study team

without indication, which type of FMT is provided. Only the patient number will be on the label. Both the patient and the study team (clinical team, study coordinator, data analyst) will be blinded to group assignments.

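### Section 1.1 plans to randomize 30 patients; sections 5.7.1 and 5.8.1 plan to randomize 36

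*Combined protocol and SAP*

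**What the plan says.** Section 1.1 (Study Design) gives the size of the trial in one sentence: "We plan to randomize 30 patients". It gives no split by group and no attrition allowance.

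Section 5.7.1 (Sample size and power calculations) sets a different target: "we plan to recruit until we have randomized 36 eligible patients (18 per FMT" group). It goes on: "With a 20% attrition rate we assume that 15 patients per group will finish the intervention". The basis is stated as: "Our sample size is determined based on current literature, feasibility and the experience of team members, due to the pilot nature of the proposed study". No effect size, standard deviation or power is given.

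Section 5.8.1 (Randomization list and blinding) agrees with 5.7.1: "The list will be created to randomize 60 patients, even though 36 are planned to be randomized". It explains the longer list by saying that "this will allow us to randomize additional patients, in case the FMT is not conducted in participants after they were randomized". The participant withdrawal criteria in section 1.3.1 say the same of patients who cannot be given the transplant: "These patients will be replaced through additionally randomized patients".

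**The concern.** The number to randomize is a basic design figure, and the protocol states it as both 30 and 36. Because no power calculation stands behind the sample size, the stated number is the plan's only commitment on size. Section 5.7.1 also makes it the point at which recruitment ends. Someone working from section 1.1 would stop six patients sooner than someone working from section 5.7.1. Stopping at either number could be described as following the protocol, and a later reader could not tell whether a trial that ended at 30 was complete or had stopped short.

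**Working it through.** **Inputs**

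- Number to randomize: 30 (section 1.1); 36, as 18 per group (section 5.7.1); 36 (section 5.8.1).
- Attrition 20%, with 15 per group expected to finish (section 5.7.1).
- List length 60 (section 5.8.1), drawn up as a "blocked randomization list (4 patients per block").
- Undosed patients are replaced by further randomization (withdrawal criteria in 1.3.1; section 5.8.1).

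**Where 36 comes from.** Expected finishers: 2 × 15 = 30. Inflating by 20% gives 30 × 1.20 = 36, the figure in 5.7.1 and 5.8.1. Dividing by the share retained gives 30 / 0.80 = 37.5, so 36 is the simple inflation. Read forwards, 18 × 0.80 = 14.4 per group, slightly under 15; going from 18 to 15 is 1 − 15/18 = 16.7% attrition. This is a rounding matter and plays no part in the contradiction.

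**Size of the gap.** 36 − 30 = 6 patients; 6/36 = 16.7% and 6/30 = 20%.

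**Can replacement reconcile the two figures?** The list has 60 − 36 = 24 places beyond the planned 36, and section 5.8.1 reserves the extra length for replacing undosed patients. Replacement therefore moves the count above 36 and cannot bring it down to 30.

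**Expected finishers under each number.** The documents do not say how the 20% divides between losses before dosing (replaced) and after dosing (not replaced). Let p be the share of all randomized patients lost before dosing, counted within the 20%, and let n be the planned number per group with undosed patients replaced. Then n/(1 − p) per group are actually randomized, and finishers per group = 0.80 × n/(1 − p).

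| Planned total | n per group | p = 0 | p = 0.04 | p = 0.20 |
|---|---|---|---|---|
| 30 | 15 | 12.0 | 12.5 | 15.0 |
| 36 | 18 | 14.4 | 15.0 | 18.0 |

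A planned 30 reaches the stated 15 per group only if every loss occurs before dosing and is replaced. In that case the number actually randomized is 30 / 0.80 = 37.5, so 30 would be a count of dosed patients and not of patients randomized.

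**Blocks.** 36/4 = 9 complete blocks; 30/4 = 7.5, so recruitment would end in the middle of a block. This is only supporting evidence for 36.

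**The case against.** The strongest reply is that this is a slip in a summary sentence. Only section 5.7.1 is worded as a rule for ending recruitment, the section governing the allocation list agrees with it, and section 1.1 is a brief overview. The list of 60 places covers either number. With no power claim in a pilot study, six patients more or fewer invalidate no stated power or error rate. The 12 per group is a worst case, and the range for 30 extends up to the stated 15. Finishing the intervention could also mean simply being dosed, since there is a single administration, which makes the table of finishers less certain.

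Much of this is fair. A shortfall in finishers is possible but not established, and the agreement of two detailed sections makes 36 the more likely intention. None of it removes the conflict: section 1.1 speaks of randomizing, as do the other two, and nothing in the documents says which prevails. Reading the finishers as dosed patients does not turn 30 into a number randomized either. The absence of a power calculation limits the statistical harm, but it also leaves the stated number as the only definition of the trial's size.

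**Conclusion.** The contradiction stands: 30 in section 1.1 against 36 in sections 5.7.1 and 5.8.1, a difference of six patients (17% of 36, 20% of 30). It rests on no assumption about attrition, because all three passages state a number to randomize. The consequence for finishers does depend on an assumption: 12 to 15 per group from 30, and 14.4 to 18 from 36, according to how the 20% falls before or after dosing. That section 1.1 carries the expected number of finishers fits the arithmetic but is not stated anywhere. As a planned enrolment figure that also fixes the end of recruitment, this must be corrected.

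**What to change.** The sponsor confirms the intended number and makes sections 1.1, 5.7.1 and 5.8.1 agree.

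- If it is 36, section 1.1 should give 36 patients to randomize, 18 per group, with the number expected to finish in a separate sentence.
- If it is 30, sections 5.7.1 and 5.8.1 must change, together with the expected number of finishers.
- In either case, because undosed patients are replaced, the sponsor states whether the number counts all randomized patients or only dosed patients, and uses that definition in all three sections.

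If 36 is confirmed, the cost is wording only: no extra patients, and no change to the randomization list, the design or the analysis.

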### **1.2 Outcomes**

#### Main outcome: Insulin resistance (HOMA-IR)

Secondary outcomes: weight (absolute number, BMI, % change), appetite score, quality of life, anxiety and depression scores

*Other measurements:* HbA1c, C-peptide, IM in stools (composition and metagenome), amount of selected groups of microorganisms measured by qPCR, blood lipids, gut hormones, blood pressure, physical examination, food intake (energy and % of energy from fat, carbohydrates, protein, fiber intake (g/d)), physical activity (units/day), environmental questionnaire, stool and serum metabolomics.

### **1.3 Study Participants**

#### 1.3.1 Patients receiving intervention

Inclusion criteria: Morbidly obese men and women, age 18 years or older, fulfilling the 1991 NIH criteria (BMI >40 kg/m^2 or BMI >35–40 kg/m^2 with other severe weight loss responsive comorbidities) (12, 36), who were referred to the Bariatric Clinic at the Toronto Western Hospital for weight loss surgery, but declining or deferring the surgery, will be included. Will accept also patients fulfilling same criteria above who are approaching us via other streams like MTOP website, cinicaltrials.gov and flyers posted in Hospitals and Universities. Patients have to be insulin resistant, which is defined as having a HOMA-IR value >2.73 (129).

*Exclusion criteria:* Regular intake of: non-steroidal anti-inflammatory drugs; immune-suppressed subjects for any reason (due to diseases or medications like steroids and other immune-suppressant agents); iron supplements; prebiotics or probiotics from other than food sources, antibiotics, or any experimental drug in the 3 months prior to study entry; type 1 or type 2 diabetes, severe chronic gastrointestinal diseases, previous gastrointestinal surgery modifying the anatomy, smoking; pregnancy or breastfeeding.

#### Participant withdrawal criteria:

#### All participants:

Any participant may discontinue from the study at any time:

- At the discretion of the investigator
- At the request of the participant (drop-out)

The reason for discontinuation will be clearly documented in the relevant Case Report Form (CRF).

The following will result in withdrawal of a participant from the study:

- Significant non-compliance with the protocol, based on the investigator's judgment following discussion with the study team and/or a co-investigator
- Any other situation where, in the opinion of the investigator, continued participation would NOT be in the best interest of the participant.

In the event that the participant discontinues the study due to a serious adverse event (SAE), a follow-up contact will be made. This contact will be documented in the source document.

If a participant fails to appear for a follow-up examination, up to three documented phone calls and/or registered mail will be used to locate and recall the participant, if possible.

Specific criteria for FMT recipients: Only one single dose of study product will be administered. Patients will be withdrawn from the study, if the FMT cannot be administered for any reasons. Data of these patients will not be included in the study, except for comparison with the patients who did receive the FMT. These patients will be replaced through additionally randomized patients. There will be no follow-up for patients who did not receive FMT.

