### 5.7.2 Statistical analysis plans

A descriptive summary of all measurements will first be compiled using appropriate graphical representations, and means, standard deviations and proportions will be calculated. Baseline characteristics of the randomized groups will be compared to ensure balance on the important variables (e.g. HOMA, BMI). Trajectory plots will be created to examine visually the changes over time.

The changes in the outcome variables of (HOMA-IR, weight, scores for appetite, quality of life, anxiety, and depression) within the two FTM groups (allogenic vs. autologous) will be compared using generalized linear mixed models (GLMM), where the within and between groups changes over time will be examined simultaneously. Factors with known influence on the outcomes will be examined for possible inclusion in our multivariate models as covariates, particularly if found imbalanced between the randomized groups. For patient drop-out, we will check missingness patterns and employ appropriate methods of handling missing data (181). The relationships between changes in outcomes and IM will first be investigated using correlation analysis (Spearman and Pearson correlation coefficients, Chi-square and Fischer exact tests as appropriate), and subsequently using methods for correlated data when considering multiple measures (incl. covariates, multiple time points, etc.). For the latter, we will employ generalized linear and nonlinear mixed models, as well as the generalized estimating equations approach. Goodness-of-fit tests will be applied for model diagnostics (182). In addition, principal component analysis (183), co-inertia analysis will be considered when investigating possible strategies for dimension reduction (where large numbers of variables may be correlated).

Statistical analyses will be performed using SAS 9.4 and R 3.2 (or subsequent versions as they become available), and all tests will be two-sided with a significance level of 5%. Where necessary, p-value adjustments for multiple testing (e.g. Holm's Bonferroni Step-down, Benjamini and Hochberg False Discovery Rate) will be employed (184).

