### 5.7.3 Selection of subjects included in the analysis

As this is a single-dose treatment, we will only include dosed subjects into the analysis. In the initial analysis, all dosed subjects will be included, followed by a per-protocol analysis.

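### Mandatory withdrawal for non-compliance also covers patients already given the single FMT, with no provision to keep collecting their outcomes, so the all-dosed analysis moves toward per-protocol

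*Combined protocol and SAP*

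**What the plan says.** The withdrawal criteria in Section 1.3.1 have a block for all participants and a block specific to FMT recipients.

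- The mandatory list in the first block opens with "The following will result in withdrawal of a participant from the study". Its first item is "Significant non-compliance with the protocol, based on the investigator's judgment following discussion with the study team and/or a co-investigator". No definition or threshold is given.
- The same block separately allows discontinuation at the investigator's discretion, at the participant's request, and where continuing would not be in the participant's interest.
- On contact after discontinuation it says only: "In the event that the participant discontinues the study due to a serious adverse event (SAE), a follow-up contact will be made".
- For a missed follow-up visit, "up to three documented phone calls and/or registered mail will be used to locate and recall the participant, if possible".
- The block for FMT recipients states: "Only one single dose of study product will be administered". It also excludes data, provides for replacement and ends follow-up, but only for undosed patients: "There will be no follow-up for patients who did not receive FMT".

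Section 5.7.3 sets the analysis populations: "In the initial analysis, all dosed subjects will be included, followed by a per-protocol analysis". The per-protocol set is not defined. Section 5.7.2 plans a generalized linear mixed model over the repeated visits and promises suitable handling of missing data after drop-out, without naming a method or a sensitivity analysis. Sections 7.2.2 and 7.3 record adverse events and serious adverse events from consent until the participant leaves the study.

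**The concern.** Where dosing is repeated, withdrawal for non-compliance at least stops further treatment. Here the whole treatment is given in one colonoscopy. After that, withdrawal for non-compliance can only end participation, including whichever of the 1- and 3-month assessments remain.

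Non-compliant dosed patients are the ones who should distinguish the all-dosed analysis from the per-protocol analysis. If their later outcomes are not collected, the first analysis loses part of what separates it from the second.

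The loss would follow from behaviour after randomisation and from an undefined judgment, and either may be related to HOMA-IR or weight. Recording of new adverse events would also stop for a patient who has received the product.

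**Working it through.** **1. The plan's own figure.** Section 5.7.1 gives 36 randomised (18 per group), 20% attrition and 15 per group finishing.
- 30 × 1.2 = 36 reproduces the stated total.
- Dividing instead gives 30/0.8 = 37.5, so 38.
- Going forward, 18 × 0.8 = 14.4 per group, against the stated 15 (attrition of 3/18 = 16.7%).
- These differences are too small to matter here. The plan gives no effect size, SD, power or rate of non-compliance withdrawal.

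**2. The texts side by side.**
- Withdrawal is mandatory, is from the study, and applies to all participants, so dosed patients are covered.
- No section says that a withdrawn dosed patient keeps the 1- and 3-month visits. The stated contact after discontinuation concerns serious adverse events, and the recall procedure concerns missed visits.
- No section says that data gathered before withdrawal are discarded.
- Loss of later outcomes is therefore an inference from a mandatory rule plus silence on follow-up. Loss of earlier data is not supported.

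**3. Weight of one patient.** 1/18 = 5.6% of an arm as randomised.

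**4. Illustrative shift.** Assume 2 of 15 patients in one arm are lost, none in the other, and their mean change is 1 SD worse than that of the other 13.
- Shift in that arm's mean: (2/15) × 1 SD = 0.133 SD.
- Standard error of the difference at 15 per arm: √(2/15) = 0.365 SD.
- Ratio: 0.133/0.365 = 0.37, a little over a third of one standard error.

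**5. What the mixed model recovers.** A simulation was run under assumed conditions: no true effect, 18 per arm, correlation 0.6 between the 1- and 3-month changes, and withdrawal in one arm only, with a tendency to withdraw that correlates 0.5 with a poor 3-month outcome. Bias in the 3-month difference, in SD:

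| Withdrawn of 18 | Patients simply absent | 1-month value kept, likelihood analysis |
|---|---|---|
| 1 | −0.06 | −0.04 |
| 2 | −0.10 | −0.06 |
| 3 | −0.14 | −0.09 |
| 4 | −0.18 | −0.12 |

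Keeping the 1-month value removes about a third of the bias (for four withdrawals, 1 − 0.121/0.181 = 0.33).

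**6. Precision.** If one to three withdrawals came on top of the planned attrition, completers would fall from 30 to 29–27. The interval would widen by √(30/29) = 1.017 to √(30/27) = 1.054, that is 2% to 5%. If they fall within the 20% allowance, nothing is lost relative to plan.

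**The case against.** A reader might infer that dosed patients' outcomes are lost altogether and that the all-dosed analysis turns into the per-protocol one. The documents do not support that. The sentences on data exclusion and on no follow-up are confined to undosed patients. Section 5.7.3 keeps every dosed subject in the initial analysis, and the mixed model can use baseline and any 1-month data. The two analyses would coincide only if every such withdrawal came before the 1-month visit, or if withdrawn patients' data were dropped.

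Nor can one say that the model is unable to correct the problem. If missingness depends only on observed data, a correctly specified likelihood analysis is valid. Otherwise, as in the simulation, it helps in part.

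Several further points stand:
- The rule may bite rarely. Diet advice is brief counselling (Section 1.4) with no stated adherence rule, and the medication limits in Section 1.3.1 are entry criteria.
- A patient who does not attend is missing whatever the withdrawal rule says.
- The clause also reaches patients before dosing, where the separate rule for undosed patients applies, and it may cover donors.
- Patients and study team are blinded (Section 5.8.1), so removal knowingly by arm should not occur. Equal losses in both arms with the same relation to outcome would largely cancel in the difference.

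Blinding does not settle the matter, however. It does not prevent missingness related to outcome. Section 7.1 lists insulin resistance, HbA1c and weight at 1 and 3 months under safety evaluations, so those judging compliance may know the 1-month results. Nothing in the plan commits the team to collecting the later outcomes of a dosed patient withdrawn under this rule.

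**Conclusion.** The concern holds in a limited form. Followed as written, the rule withdraws dosed patients for non-compliance when no treatment remains to be stopped, and the plan provides no outcome collection afterwards. This moves the all-dosed analysis toward the per-protocol analysis without making them the same, and the mixed model can be relied on to correct the resulting bias only in part.

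The size is unknown because the documents give no number of such withdrawals, and it may be small. The 0.13 SD shift rests on an assumed count, an assumed 1 SD difference and losses confined to one arm. The simulated biases of 0.04 to 0.18 SD also rest on assumptions. Neither is a prediction. Unresolved adverse events are still to be followed under Section 7.2.2; what would stop at study exit is the recording of new ones.

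This is a cheap improvement, not evidence that the main analysis fails.

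**What to change.** Amend the withdrawal criteria in Section 1.3.1 as follows:

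1. Non-compliance after dosing is recorded as a protocol deviation and does not by itself end participation.
2. Such deviations are used only to define the per-protocol set, which is fixed before unblinding.
3. The 1- and 3-month assessments continue, and their results enter the all-dosed analysis, unless the participant withdraws. Adverse event recording then continues as well.
4. The general investigator-discretion clause is stated not to be a route for non-compliance withdrawals after dosing. Otherwise the same judgment-based removal stays possible.

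The participant-request clause, the best-interest clause and the rule for undosed patients stay unchanged. Whether a patient should stop for their own welfare is a clinical matter and is not touched.

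The cost is a wording change and a few additional follow-up visits. Patients who do not attend will still be missing, so the change reduces the problem without removing it.

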#### 7.2.1 Adverse Event Definition

An AE is defined as any untoward medical occurrence in a subject or clinical investigation subject administered a pharmaceutical/medicinal product. An AE does not necessarily have to have a causal relationship with this treatment.

An AE can therefore be any unfavorable and unintended sign (including a clinically significant abnormal laboratory finding, for example), symptom, or disease temporally associated with the use of a medicinal product (investigational or marketed), whether or not considered related to treatment with the medicinal product.

An AE includes:

- An exacerbation of a pre-existing illness, sign, symptom, or clinically significant (as determined by the investigator) laboratory test abnormality
- An illness, sign, symptom, or clinically significant laboratory abnormality that is detected or diagnosed after study drug administration
- Pretreatment or post treatment events that occur as a result of protocol-mandated procedures

An AE does not include:

• The disease or disorder being studied or signs and symptoms associated with the disease or disorder, unless there is worsening of the condition of the disease or disorder

Although an overdose of the study drug or concomitant medication without any clinical sign or symptom is not technically an AE, it should be captured as AE to provide valuable safety data on higher untested doses of study drug.

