#### 7.2.2 Procedures for Reporting Adverse Events

Adverse events may be spontaneously reported, obtained through non-leading questioning of a subject. Adverse events will be recorded from the signing of informed consent until the study participant exits the study.

Adverse events do not require expedited reporting. They will be documented on the appropriate case report form/source document. During the duration of the study, the participants will be directed to report any AEs the study team. For more details on documentation and reporting guidelines, see UHN REB Unanticipated Problem Reporting Guidance (*document enclosed*).

At each visit, new AEs are recorded sequentially. The AE term should note the diagnosis whenever possible, not the individual signs or symptoms (e.g., myocardial infarction should be recorded rather than chest pain, and elevated cardiac enzymes). Also recorded are:

- Start and stop date and time
- Whether or not the event is continuing
- Frequency (intermittent, continuous)
- Intensity (mild, moderate, severe)
  - o Mild: usually transient, requiring no special treatment and generally not interfering with usual daily activities
  - o Moderate: usually ameliorated by simple therapeutic maneuvers and impairs usual activities

o Severe: requires vigorous therapeutic intervention and interrupts usual activities. Hospitalization may or may not be required.

- Relationship to study drug (not related, related): identify relationship as "related" if a causal relationship between the investigational product and an AE is at least a reasonable possibility (i.e., the relationship cannot be ruled out).
- Whether or not the AE is serious (i.e., an SAE). If identified as an SAE, the AE should be reported as described below
- Actions taken (none, study drug dose interrupted, study drug discontinued, other medication change, non-drug therapy).
- Outcome (resolved, severity or frequency increased, ongoing, and fatal). An individual AE receives only one outcome.

Adverse events not resolved at the end of treatment will be followed until resolution or until the AE is judged by the investigator to have stabilized.

Laboratory values and clinical findings at the scheduled examinations must be reported as AEs if they:

- Are considered clinically significant by the site investigator,
- Fulfill SAE criteria, and/or
- Cause subject discontinuation from the study.

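### Patients who start bowel preparation or colonoscopy but are not dosed have no planned adverse-event follow-up after withdrawal (beyond one contact for an SAE discontinuation) and fall outside the only defined analysis set

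*Combined protocol and SAP*

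**What the plan says.** The participant withdrawal criteria in section 1.3.1 set four rules for recipients who are not dosed:

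- Withdrawal: "Patients will be withdrawn from the study, if the FMT cannot be administered for any reasons".
- Data: "Data of these patients will not be included in the study, except for comparison with the patients who did receive the FMT".
- Replacement: "These patients will be replaced through additionally randomized patients".
- Follow-up: "There will be no follow-up for patients who did not receive FMT".

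The general part of the same section has the reason for any discontinuation entered in the CRF and provides one documented contact when a participant discontinues because of an SAE.

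The safety sections set a wider scope. Section 7.2.1 includes among AEs "Pretreatment or post treatment events that occur as a result of protocol-mandated procedures". Sections 7.2.2 and 7.3 record AEs and SAEs from consent until the participant leaves the study. Section 7.2.2 also states: "Adverse events not resolved at the end of treatment will be followed until resolution or until the AE is judged by the investigator to have" stabilised.

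On analysis, section 5.7.3 says "we will only include dosed subjects into the analysis": first all dosed subjects, then a per-protocol analysis. No separate safety set is defined.

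**The concern.** Randomisation comes before stool collection, bowel preparation and colonoscopy (section 1.5), and the filtrate is infused only as the colonoscope is withdrawn (section 1.4.3). A patient can therefore go through laxatives, 4 L of polyethylene glycol, insertion of the colonoscope and an ileal biopsy and still not be dosed. One possible reason is a complication of those steps.

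If follow-up and analysis both depend on having been dosed, membership of the analysed group depends partly on the absence of a procedural harm. A safety summary of dosed patients would then lean towards no procedural harm. Any event that appears or develops after withdrawal may never be seen. Section 7.1 gives continuous subject safety and the overall safety profile of FMT as aims of the safety evaluation, and both would be weakened in the same patients.

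**Working it through.** **The plan's own figure.** The documents give no expected number of undosed patients and no rate of procedural complications, so there is no stated figure to reproduce. What can be checked is how the rules combine.

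**Step 1: what happens to an undosed patient under the text.**

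- From consent to withdrawal: AEs and SAEs are recorded (7.2.2, 7.3), including pretreatment events from study procedures (7.2.1). The reason for discontinuation goes in the CRF (1.3.1). An event that itself prevents dosing falls in this window and is captured.
- At withdrawal: leaving the study closes the AE and SAE recording window (7.2.2, 7.3).
- After withdrawal, if the reason was an SAE: one contact (1.3.1).
- After withdrawal, otherwise: nothing is planned. The symptom diary starts after FMT (1.5), and AEs are assessed at visits (7.1), which an undosed patient does not have. The patient may telephone the team (7.1), but that depends on the patient.
- Open AEs: the follow-to-resolution rule in 7.2.2 is tied to the end of treatment. An undosed patient has no treatment to end, and the text does not say whether that rule or the no-follow-up rule in 1.3.1 prevails.
- Analysis: outside the set defined in 5.7.3. Section 1.3.1 allows a comparison with dosed patients, but no safety comparison is specified.

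**Step 2: which procedures can precede a failure to dose.** Bowel preparation and insertion always come before infusion. Section 1.4.3 keeps filtrate out of the ileum because of the biopsy there, which implies that the ileal biopsy comes first. The order of the colonic and rectal biopsies relative to infusion is not stated.

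**Step 3: scale.** Section 5.8.1 provides a list of 60 places for 36 planned patients: 60 − 36 = 24 spare places. This is a ceiling on replacements, not a forecast. Assumed examples with 36 dosed patients:

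- 2 undosed: 2/38 = 5.3% of those randomised
- 4 undosed: 4/40 = 10.0%
- 8 undosed: 8/44 = 18.2%

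Some of these patients might never start bowel preparation, so the shares do not measure procedural harm.

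**Step 4: effect of one omitted event (illustration).** Assume replacement continues until 36 are dosed, none of them has a procedural complication, and one undosed patient has one.

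- Dosed only: 0/36 = 0%. One-sided 95% upper bound = 1 − 0.05^(1/36) = 0.080, or 8.0%.
- All who started preparation: 1/37 = 2.7%. The exact one-sided 95% upper bound p solves (1 − p)^37 + 37p(1 − p)^36 = 0.05. At p = 0.122 the terms are about 0.008 and 0.042, which sum to 0.050, so the bound is 12.2%.

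Like for like, the estimate moves from 0% to 2.7% and the upper bound from 8.0% to 12.2%. Section 1.1 gives 30 as the number to randomise, against 36 in 5.7.1 and 5.8.1; the reasoning is the same with either.

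**The case against.** The strongest reply is that the safety record is not switched off for undosed patients. A harm that stops dosing must occur before withdrawal, so it is recorded as an AE or SAE, and the reason for leaving is documented. This stands. A reader might infer that procedural harms vanish from the record exactly when they prevent dosing, but sections 7.2.1, 7.2.2 and 7.3 do not support that. The gap concerns later events, the course of open non-serious AEs, and tabulation.

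Second, follow-up may simply mean the visits after FMT, which is how sections 1.4 and 1.4.4 use the idea. This is a plausible reading, but the text does not state it, and the sentence carries no such limit.

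Third, section 5.7.3 sits among statistical methods whose named outcomes are HOMA-IR, weight and questionnaire scores, so AE tables might still include undosed patients. Nothing forbids this, but nothing provides for it either: the only set defined is dosed subjects.

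Fourth, section 1.3.1 does not say when withdrawal takes effect, and section 1.4.2 keeps post-procedure observation under standard practice. It would therefore be wrong to say that such patients leave on the day or lose medical care.

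Fifth, a reader might turn the 24 spare places into a claim that 24/60 = 40% of randomised patients would go unobserved. That figure is list capacity only.

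Finally, section 7.2.2 rates causality against the study product alone. A procedural event in someone who never received the product is correctly rated unrelated, so this is a limitation of the form and not a contradiction.

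**Conclusion.** The point holds as a conflict that needs to be reconciled. Followed literally, the plan has no arrangement to detect a delayed event, or to follow an open non-serious AE, in a patient who started study procedures but was not dosed. After an SAE discontinuation it offers one contact. Events that were recorded in such patients have no place in a defined analysis set. Because a procedural complication can be the reason for not dosing, these omissions need not be random.

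The frequency cannot be derived from the documents. The step from 0/36 to 1/37 shows only that, in a trial of this size, one event separates none observed from observed. It rests on the assumed counts above. The conclusion itself needs no rate: it rests on reading sections 1.3.1 and 5.7.3 as written against 7.2.1, 7.2.2 and 7.3. It does not touch the efficacy comparison. It should be corrected by amendment.

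**What to change.** Reconcile sections 1.3.1 and 5.7.3 with 7.2.1, 7.2.2 and 7.3:

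1. In 1.3.1, state that the absence of follow-up for undosed patients refers to the efficacy visits. State that AE and SAE recording, and the existing 7.2.2 rule for unresolved AEs, apply to anyone who has started a study procedure. Word that rule so that it does not depend on reaching the end of treatment.
2. In 5.7.3, define a safety set of all patients who start bowel preparation, tabulated as dosed and undosed. Keep the dosed-only set for efficacy.
3. Optionally, in 7.2.2, record relationship to protocol procedure (bowel preparation, colonoscopy, biopsy) beside relationship to study product.

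The cost is amendment wording, one extra safety table and a few contacts by the existing coordinator, plus one CRF field if item 3 is adopted. The efficacy analysis is unchanged.
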